The hypothesis is that TaTME will be non-inferior in mesorectum specimen quality and involved CRM and therefore will result in comparable rate of local recurrence. After TaTME which allows direct endoscopic visualisation we expect less morbidity due to less conversion rates and better anastomotic techniques. Moreover, the TaTME procedure will potentially enable more sphincter saving procedures. These expected results will have positive effect on functional outcome and health related quality of life.

FUNDING AND SUPPORT IN KIND

FUNDER(S) (Names and contact details of ALL organisations providing funding and/or support in kind for this trial)	FINANCIAL AND NON FINANCIAL SUPPORT GIVEN

KEY TRIAL CONTACTS

Trial Governors	Prof [name] (Chair Department of Surgery, VU University Medical Centre, Amsterdam) Prof [name] (Chief of Department of Gastrointestinal Surgery, Hospital Clinic, Barcelona) Prof [name] (Head of Division of Surgery, Imperial College, London)
Trial Co-ordinator	[name], [name]
Trial Contacts	[name], [name] VU University Medical Centre Department of Surgery [name], The Netherlands Email: [contact] [contact] [contact]
Protocol and Writing Committee	[name], [name], [name], [name], [name] , [name], [name], [name], [name], [name], [name], [name]
Statistician	[name]
COLOR III study group	All included centres; Follows

LIST OF CONTENTS

[figure not shown]
GENERAL INFORMATION	Page
TITLE PAGE	1
RESEARCH REFERENCE NUMBERS	2
SIGNATURE PAGE	3
TRIAL SYNOPSIS	4
TRIAL SUMMARY	5
FUNDING	7
KEY TRIAL CONTACTS	8
LIST OF CONTENTS	9
LIST OF ABBREVIATIONS	10
TRIAL FLOW CHART	12
STUDY PROTOCOL	
1. BACKGROUND	13
2. RATIONALE	16
3. OBJECTIVES AND OUTCOME MEASURES/ENDPOINTS	17
4. TRIAL DESIGN	19
5. ELIGIBILITY CRITERIA	22
6. PERIOPERATIVE CARE AND EXAMINATION	23
7. INVESTIGATIONAL PRODUCT	24
8. NON-INVESTIGATIONAL PRODUCT	25
9. SURGICAL PROCEDURE	26
10. (HISTO)PATHOLOGY	28
11. POSTOPERATIVE TREATMENT	30
12. FOLLOW-UP	31
13. RECURRENT DISEASE	32
14. STATISTICS AND DATA ANALYSIS	33
15. ADMINISTRATIVE ASPECTS, MONITORING AND PUBLICATION	34
16. SAFETY REPORTING	37
17. ETHICAL AND REGULATORY CONSIDERATIONS	43
18. REFERENCES	45
19. APPENDICES	48

LIST OF ABBREVIATIONS

AE	Adverse Event
APR	Abdominoperineal Resecton
AR	Adverse Reaction
cCRM	Clinical Circumferential Resection Margin
CI	Chief Investigator
CRF	Case Report Form

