A systematic review was performed by our study group including large randomised trials for laparoscopic and/or open surgery for rectal cancer. Only randomised trials reporting involvement of CRM, local recurrence rate after 3 years and including 100 patients or more in one arm were included. We searched in Pubmed Medline and OVID Embase. Mesh terms we used were: "Colorectal neoplasms" [majr] OR ((colorectal OR rectal OR rectum OR rectosigmoid) AND (cancer* OR carcinoma* OR adenocarcinoma* OR malignan* OR tumour* OR tumour* OR neoplasm*)) AND ((local[ti] OR transanal*[ti] OR rectoscop* OR endoscop*[ti] OR limited[ti]) AND (surgery OR surgical* OR resect* OR excision OR treatment OR therapy) OR microsurgery[ti] OR microsurgical* OR spts OR parks) AND (for systematic reviews) ("meta-analysis" [pt] OR "meta-anal*" [tw] OR "metaanal*" [tw] OR ("quantitativ* review*" [tw] OR "quantitative* overview*" [tw]) OR ("systematic* review*" [tw] OR "systematic* overview*" [tw]) OR ("methodologic* review*" [tw] OR "methodologic* overview*" [tw]) OR ("review" [pt] AND "medline" [tw])). In total 5 trials were included. The review showed high percentages of involved CRM. Only one large randomised trial, the COREAN trial, reported a low rate of involved CRM of 2.9%. The other randomised trials incorporating a large number of patients, reported involved CRM in 7.7% to 16% of the patients operated for rectal carcinoma. This involved CRM correlates with local recurrence after 3 – 5 years. Roughly 50% of the patients with an involved CRM, developed a local recurrence. In conclusion: the average CRM rate after abdominal rectal resection including TME is approximately 7%. Moreover, it is reported that resection of low rectal tumours results in higher rates of involved CRM compared with higher tumours.^{5,6,8,12,13,16,20-23}

Table 1. Involved CRM and LR after abdominal rectal resection (LAR + APR) - total rectum

Study/national report	RCT/report	Year	Percentage involved CRM	Percentage local recurrence	Tumour height
CLASICC	RCT	2005	Lap. 16% Open 14%	Lap. 7.8% Open 7.0% 3Y	Total rectum, only AR
Dutch TME	RCT	2007	Open 16%	5.6% 5Y after RT	0-15cm
MRC CR07	RCT	2009	Lap. + open 10%	4.4% 3Y after RT	0-15cm
	Report		Lap. + open 5.2%		Total rectum
DSCA		2014			

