3.3 Secondary endpoints/outcomes

Pathological

- Involvement of CRM (defined as tumour cells within 1mm from the lateral surface of the mesorectum, centrally reviewed by pathologists)
- Quality of specimen (as proposed and published by Quirke et al.)¹⁴
- Distal resection margin (defined as distance in cm from distal border of the tumour to distal resection surface)
- Translational research will be performed on predictive/prognostic biomarkers and imaging methods.

Clinical

- Length of hospital stay postoperatively (calculated as time from surgery to discharge in days)
- Morbidity within 28 days after surgery and within 90 days (graded by Clavien-Dindo Classification)
- Percentage of sphincter saving procedures (defined as colostomy percentage at 1 year postoperatively)
- Mortality within 28 days after surgery and within 90 days
- Local recurrence at five years (defined as cancer recurrence within the pelvic and perineal area)
- Disease-free survival at three and five years (calculated as time from surgery to last follow-up or date of recurrence)
- Overall survival at three and five years (calculated as time from surgery to last follow-up or death)

Quality of life

- Postoperative health related quality of life (quality adjusted life years) and functional outcome (measured with EORTC QLQ-CR29 and C30, EQ5D and LARS score). A difference of more than 10% in the EORTC list is considered significant.

See 'Chapter 12 Follow-up' for follow-up moments.

Costs (national) (sidestudy)

- In-hospital direct and indirect costs (measured with EQ5D and cost incremental analysis)
- Out-of-hospital postoperative costs (measured with EQ5D and cost incremental analysis)

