14 STATISTICS AND DATA ANALYSIS

14.1 Sample size calculation

The primary endpoint is the local recurrence after 3 years. In laparoscopic TME the percentage of local recurrence is estimated 5%. A local recurrence increase of 4% is believed to be inferior. Based on this difference, sample size calculation has been done with a one-sided level of significance of 2,5% and a power of 80%. A total of 1104 patients is needed, 735 patients in the TaTME arm and 369 patients in the laparoscopic TME arm.

In this sample size calculation, additional postrandomisation analyses (drop-out, cross-over total 5%), is taken into account.

Randomisation will be stratified for

- T3a and less / T3b and more
- Downstaged with chemoradiotherapy: yes / no / NA
- Preoperative radiotherapy: yes / no
- Height of the tumour: 0-2.0cm / 2.1-5.0cm / 5.1-10cm
- Gender: male / female
- BMI \leq 30.0 / BMI $>$ 30.0

The randomisation will be executed in such a way that concealment of allocation for the indicating surgeon is guaranteed.

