14.2 Statistical analysis plan

Baseline numerical data will be described in means, standard deviations or medians and interquartile ranges, baseline categorical data will be displayed in percentages. All comparative analyses will be conducted on an 'intention to treat' basis. Consequently, patients who are randomised to TaTME and converted to a laparoscopic or open TME, will be analysed in the TaTME group. Patients who are randomised to a laparoscopic resection and converted to TaTME or open TME, will be analysed in the laparoscopic group. Ninety days postoperative mortality, pathological resection margin and complication rates will be compared using the Chi-square test or an exact test if necessary. Local recurrence rate, disease-free and overall survival will be compared using the Log-rank test. Exploratory analysis of the prognostic effects of various baseline factors on disease-free survival will be carried out through multivariate Cox-regression. Apart from intention to treat analyses, per protocol analyses will be applied.

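### The protocol hypothesises that TaTME is non-inferior on involved CRM, but its planned test is one of equal proportions with no margin and cannot settle that secondary hypothesis

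*Protocol*

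**What the plan says.** Under Hypothesis in the Trial Summary: "The hypothesis is that TaTME will be non-inferior in mesorectum specimen quality and involved CRM". The same sentence goes on to infer a comparable local recurrence rate from this.

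Section 3.3 lists the outcome among the pathological secondary endpoints: "Involvement of CRM (defined as tumour cells within 1mm from the lateral surface of the mesorectum, centrally reviewed by pathologists").

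Section 14.2 names the method for it: "Ninety days postoperative mortality, pathological resection margin and complication rates will be compared using the Chi-square test or an exact test if necessary".

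The only non-inferiority margin in the protocol belongs to the primary endpoint, 3-year local recurrence (Trial Summary and 14.1): "A local recurrence increase of 4% is believed to be inferior". No margin, confidence-interval rule or power is given for CRM. Section 14.2 plans intention-to-treat and per-protocol analyses, but neither supplies a margin.

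**The concern.** A chi-square or exact test asks whether the two proportions are equal. Failure to reject leaves open any excess that the data were too few to exclude. Rejection does not show that the excess is beyond what would be tolerated. Without a margin, the test therefore cannot answer the question that the Hypothesis paragraph asks.

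The practical risk is one of timing. Pathology is known shortly after surgery, whereas the primary endpoint needs three years of follow-up. Section 15.11 holds back publication only until accrual is complete. A non-significant CRM comparison could thus appear well before the recurrence result and be presented as confirming the first half of the hypothesis. The background section gives the reason why this matters: "Roughly 50% of the patients with an involved CRM, developed a local recurrence".

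**Working it through.** **1. The protocol's own figure.** Section 14.1: 5% recurrence in both arms, 4-point margin, one-sided 2.5%, power 80%, allocation 2:1.

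Control n = (1.960 + 0.842)² × 0.05 × 0.95 × (1 + 1/2) / 0.04² = 7.849 × 0.07125 / 0.0016 = 349.5, so 350. TaTME is 700 and the total 1050. Allowing 5% loss, 350/0.95 gives 369 and 1050/0.95 gives 1106, against 369 and 1104 stated. The primary sample size reproduces.

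**2. Evaluable patients for CRM.** 735 × 0.95 = 698 and 369 × 0.95 = 351.

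**3. Control CRM rates, all from section 1.** 2.9% (COREAN laparoscopic arm, Table 2), 7% (the average stated after the systematic review), 9.4% (COLOR II laparoscopic, mid and low rectum, Table 2) and 10% (the COLOR II figure set beside the pilot series).

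**4. Chance that the chi-square test is non-significant when TaTME is truly worse by d.** With control rate p, TaTME rate q = p + d and pooled rate r:

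- s0 = √[r(1 − r)(1/698 + 1/351)]
- s1 = √[q(1 − q)/698 + p(1 − p)/351]
- miss rate ≈ 1 − Φ[(d − 1.96 s0)/s1] (the opposite tail is negligible)

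Example, 7% v 11%: r = (698 × 0.11 + 351 × 0.07)/1049 = 0.0966, s0 = 0.01933, s1 = 0.01805. Then (0.04 − 1.96 × 0.01933)/0.01805 = 0.117, Φ = 0.547, and the miss rate is 45%.

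| Control rate | d = 4 points: formula | simulation | d = 8 points: formula | simulation |
|---|---|---|---|---|
| 2.9% | 20.9% | 19.6% | 0.1% | 0.1% |
| 7% | 45.3% | 44.7% | 2.4% | 2.3% |
| 9.4% | 53.5% | 52.9% | 5.1% | 5.0% |
| 10% | 55.1% | 54.5% | 5.9% | 5.8% |

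(Simulation: 400,000 trials per cell, uncorrected chi-square.)

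With all 735 v 369 patients, the formula for 4 points gives 19%, 43%, 51.5% and 53%. With a continuity correction and about 698 v 350, simulation gives about 50% at 7% and 57% at 9.4%.

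**5. Which excess matters.** The 4 points are borrowed from the recurrence margin. If about half of involved margins lead to local recurrence, 4 points of CRM correspond to 4 × 0.5 = 2 points of recurrence, and the 4-point recurrence margin corresponds to 4/0.5 = 8 points of CRM.

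**6. What an interval rule would deliver.** With equal true rates and margin m, power ≈ Φ(m/s − 1.96), where s = √[p(1 − p)(1/698 + 1/351)].

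- m = 4 points: at 7%, s = 0.01670 and power is 67% (68% simulated); at 10%, s = 0.01963 and power is 53%.
- m = 8 points: 98% or more across control rates of 7-10% (about 99% simulated).
- If the true excess equals the margin, the rule wrongly claims non-inferiority about 2.1-2.2% of the time in simulation at those control rates.

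**The case against.** The strongest reply is that CRM is not a formal non-inferiority endpoint. Non-inferiority is made operational only for local recurrence, and CRM appears in 3.3 without any criterion. The Hypothesis paragraph can be read as biological rationale, and the conclusion of the background section puts the same idea as comparable, not non-inferior. A test of difference is a common default for a secondary endpoint. It also suits the CRM hypothesis in 14.3, which expects more involved margins with laparoscopy in tumours at 0-5 cm. Margins and reporting rules for secondary endpoints are often left to a statistical analysis plan, which is not at hand here.

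Much of this stands, and it limits the point to a secondary endpoint. It does not remove the point: the protocol is not silent, since it states one hypothesis and names a test for another. An analysis plan that followed 14.2 would inherit the mismatch.

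Four stronger readings are tempting and are not supported:

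- *That the trial will claim non-inferior margins from p > 0.05.* No section says so, and naming a test does not bar reporting a risk difference with its interval.
- *That a relevant excess would be missed about half the time.* This holds only for a 4-point excess at control rates of about 7-10%. At 2.9% the miss rate is about one in five, and for 8 points it is about 6% or less.
- *That 90-day mortality and complications share the fault, because the same sentence covers them.* No non-inferiority hypothesis is stated for them. The Hypothesis paragraph expects less morbidity, and a difference test can address that.
- *That CRM carries the trial's main conclusion.* The DSMB charter in 16.3 does call it the primary endpoint, but the synopsis, 3.2 and 14.1 all fix local recurrence. That inconsistency is a separate matter.

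**Conclusion.** Wrong as written, for a secondary endpoint. The Hypothesis paragraph and 14.2 do not fit together: non-inferiority on involved CRM is hypothesised, and the only stated analysis is a test of equality without a margin. The mismatch itself rests on the text alone.

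The size of the risk depends on assumptions: a two-sided 5% level for the chi-square test (none is stated), 5% loss, the control rate, and the excess regarded as important (the protocol sets none for CRM). Over the protocol's own control rates, the chance of a non-significant result runs from about 20% to 55% for a true 4-point excess, and from near zero to about 6% for 8 points. The 5% loss slightly overstates these figures, because 14.1 counts cross-over within it and crossed-over patients still yield a specimen.

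**What to change.** In 14.2, state that involved CRM will be reported as the risk difference (TaTME minus laparoscopic) with its two-sided 95% confidence interval. State that non-inferiority on CRM will be concluded only if the upper limit lies below a single margin, and that a non-significant chi-square or exact test is not evidence of non-inferiority. Fix the margin, with its justification, before the CRM data are analysed. The chi-square test may stay as a descriptive comparison and for the 14.3 hypothesis.

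If no CRM margin can be agreed, reword the Hypothesis paragraph in the Trial Summary so that it does not claim non-inferiority on CRM.

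The cost is a few sentences and the choice of a margin, with no extra patients or data. The downside is that a tight margin may leave the CRM claim inconclusive: with equal true rates and control rates of 7-10%, power is about 53-68% at 4 points and about 99% at 8 points.

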The aim is to show non inferiority of TaTME compared to standard laparoscopic TME for mid and low rectal cancer local recurrence after 3 years of follow-up as primary endpoint. Secondary endpoints include morbidity and mortality, residual mesorectum on postoperative MRI, pathology, disease-free and overall survival, percentage of sphincter saving procedures, functional outcome and quality of life.

Statistics and randomisation

This trial is designed as a non-inferiority trial. The expected percentage of patients with a local recurrence after laparoscopic TME surgery is 5% after 3 years. TaTME is believed to be inferior to laparoscopic TME when there is a difference in local recurrence rate of more than 4% after 3 years in favour of conventional TME. Therefore, sample size is calculated based on non-inferiority with a difference of 4% with a one-sided level of significance of 2,5%, a power of 80% and a 5% drop-out rate. A total of 1104 patients is needed, 735 patients in the TaTME arm and 369 patients in the laparoscopic TME arm. Randomisation will be in a 2:1 ratio in favour of the TaTME procedure. It will be stratified for T-stage, preoperative radiotherapy, height of the tumour, gender and BMI. All analyses will be performed on intention-to-treat basis.

Main selection criteria

Patients with a histologically proved single mid or low rectum carcinoma (0-10cm from anal verge) on MRI, eligible for curative TME surgery with a intention for anastomosis, are included. Main exclusion criteria are T4 tumours, T3 tumours with a suspected involved mesorectal fascia (MRF) after neoadjuvant therapy, patients with concomitant metastases or other malignancies, with malignancies in their medical history or with signs of acute mechanical obstruction by the tumour.

Follow-up

Follow-up is based on international guidelines including imaging of the pelvis after three years with extra functional outcome questionnaires. Patients will visit outpatient clinic at least yearly for a follow-up period of five years. At the outpatient clinic the physician will carry out anamnesis and perform physical examination to check for distant metastasis and/or local recurrence. In case of the development of recurrence disease, follow-up should be pursued up to 3 years after diagnosis of recurrence.

Hypothesis

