3.2 Primary endpoint/outcome

The primary endpoint is the percentage of patients with local recurrence after 3 years of follow-up.

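### Section 14.2 names only an ordinary log-rank test for local recurrence, and as written that test does not address the 4-point, 3-year margin on which the trial is defined and sized

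*Protocol*

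**What the plan says.** The Trial Summary (Statistics and randomisation) states the design: "This trial is designed as a non-inferiority trial". In the same paragraph TaTME counts as inferior "when there is a difference in local recurrence rate of more than 4% after 3 years in favour of conventional TME". Section 3.2 fixes the outcome as a proportion at one time point: "The primary endpoint is the percentage of patients with local recurrence after 3 years of follow-up".

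Section 14.1 sizes the trial on that basis. The control rate is given as "In laparoscopic TME the percentage of local recurrence is estimated 5" per cent, and the margin follows: "A local recurrence increase of 4% is believed to be inferior". The test level is 2.5% one-sided, power is 80%, allocation is 2:1 and the loss allowance is 5%. The result is 1104 patients (735 TaTME, 369 laparoscopic).

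Section 14.2 gives the analysis: "Local recurrence rate, disease-free and overall survival will be compared using the Log-rank test". This is the only comparison named for local recurrence, and the wording is the same as for the two survival outcomes. The section mentions no margin, no estimate of the 3-year difference, no confidence limit and no shifted null hypothesis.

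**The concern.** The hypothesis and the named test do not match. The trial wants to reject a difference of 4 points or more at 3 years. An ordinary log-rank test tries to reject equality of the two hazards over the whole of follow-up. A significant result would show a difference without saying whether it exceeds 4 points. A non-significant result would show only that equality was not rejected, which is not evidence that the difference is below 4 points.

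An analyst who follows section 14.2 literally therefore ends with a p-value that does not settle the primary question, and has to supply the decision rule afterwards. In an unblinded trial of a new operation, that rule should be fixed in advance.

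**Working it through.** **Inputs.** From section 14.1 and the Trial Summary: control rate 5% at 3 years, margin 4 points, one-sided alpha 2.5% (z = 1.960), power 80% (z = 0.842), ratio 2:1, loss 5%. The TaTME rate under the alternative is not given. I assume 5%, in line with the protocol's expectation of comparable recurrence.

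**1. Which test does 1104 belong to?** Unpooled non-inferiority formula for a difference in proportions:

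- Control arm: (1.960 + 0.842)² × 0.05 × 0.95 × (1 + 1/2) / 0.04² = 349.5
- Total: 3 × 349.5 = 1048.6
- Allowing for 5% loss: 1048.6 / 0.95 = 1103.7, so 1104

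The stated figure is reproduced, which supports the 5% assumption. A superiority comparison of 5% v 9% (two-sided 5%) would need 1560. The trial was sized as a risk-difference non-inferiority test.

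**2. What that test delivers with the planned patients.** Evaluable after 5% loss: 735 × 0.95 ≈ 698 and 369 × 0.95 ≈ 351.

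- SE = √[0.05 × 0.95 × (1/698 + 1/351)] = 1.43 points
- Power = Φ(4/1.426 − 1.960) = Φ(0.845) = 80.1%
- Non-inferiority requires an observed difference below about 4 − 1.96 × 1.426 = 1.2 points

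**3. If a non-significant log-rank were read as non-inferiority.** I used 20,000 simulated trials per scenario, with 698 v 351 patients, exponential times, censoring at 3 years and no deaths:

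| True rates (TaTME v lap) | Log-rank not significant (two-sided 5%) | Upper 95% limit below 4 points |
|---|---|---|
| 5% v 5% | 95% | 81% |
| 7% v 5% | 77% | 25% |
| 9% v 5% (at the margin) | 35% | 2.3% |

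A closed-form check of the last row uses the two-proportion test:

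- Pooled rate = (698 × 0.09 + 351 × 0.05)/1049 = 7.66%; SE under equality = 1.74 points
- SE under 9% v 5% = 1.59 points
- Power = Φ[(4 − 1.96 × 1.7405)/1.5896] = Φ(0.370) = 64.4%, so 35.6% are not significant

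The event-count (Schoenfeld) approximation gives a lower figure, 27%, but the direct simulation agrees with 35%. With an assumed death rate of 4% per year the figure is 38%.

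**4. If the margin were converted to a hazard ratio.**

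- Equivalent ratio = ln(0.91)/ln(0.95) = 1.84; its logarithm is 0.609
- Events needed for 80% power at 2:1: 4.5 × (1.960 + 0.842)²/0.609² = 95.2, so 96
- Events expected at 5%: 1049 × 0.05 = 52.5, or 1104 × 0.05 = 55.2 with no loss
- SE = √(4.5/52.45) = 0.293; power = Φ(0.609/0.293 − 1.960) = 55%
- With 55.2 events: SE = 0.286; power = 57%

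**The case against.** The sentence in section 14.2 groups local recurrence with disease-free and overall survival. Section 3.3 lists 5-year local recurrence and both survival outcomes as secondary, and a log-rank test suits those. On that reading the margin test is merely left unwritten and may sit in a statistical analysis plan that is not shown. This does not hold. The Trial Summary uses the term local recurrence rate for the primary margin itself, and section 14.2 names no other analysis of local recurrence. A separate plan with a margin test would depart from the protocol's own sentence, so that sentence needs correcting either way.

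Other parts of the objection stand, and they limit the point. A reader might infer four stronger things that the protocol does not support:

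- *That a log-rank test can never test a margin.* It can be run against a hazard ratio other than 1. The protocol does not say so, and that would be a different scale from the stated 4 points.
- *That the trial has a 35% false-claim rate, or only 55–57% power.* Each figure belongs to a decision rule that the protocol does not state. They show that neither way of stretching the named test recovers the design.
- *That the two analysis sets conflict.* The Trial Summary says "All analyses will be performed on intention-to-treat basis" and section 14.2 adds "Apart from intention to treat analyses, per protocol analyses will be applied". Section 14.2 puts all comparative analyses on intention-to-treat, with per-protocol in addition. How the two combine is usual content for an analysis plan.
- *That censoring deaths is an error.* A log-rank test that censors deaths without local recurrence is a legitimate cause-specific comparison. Not naming a competing-risk method is no mistake in a protocol.

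**Conclusion.** The point holds for the test as named. Non-inferiority, the 3-year time point, the absolute 4-point margin and the one-sided 2.5% level are all fixed. The one analysis stated for local recurrence uses none of the margin, and no stated step links an estimate to it. This is a mismatch between a stated hypothesis and a stated analysis, so it goes beyond detail left for later.

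It would be wrong to conclude that the trial cannot answer its question. The defect is confined to the analysis sentence, because the planned patients already give about 80% power for the right comparison. The calculations assume a 5% TaTME rate under the alternative and 5% loss spread equally over both arms. The simulations also assume exponential recurrence times and, except where stated, no deaths. They do not model the clustering of detection around the scheduled 3-year pelvic scan.

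**What to change.** For the primary endpoint, replace the log-rank sentence in section 14.2 with wording such as:

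> *Estimate the difference (TaTME minus laparoscopic) in the 3-year local recurrence percentage with its two-sided 95% confidence interval. TaTME is non-inferior if the upper limit is below 4 percentage points.*

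Keep the log-rank test as a supportive comparison for local recurrence, and for disease-free and overall survival. Cumulative incidence with death as a competing event is a reasonable estimator of the 3-year percentages, if the team wishes to name one.

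The cost is one sentence of protocol text, carried into the analysis plan if there is one. The sample size of 1104 and the data collection do not change.
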